## 7. PRIMARY ANALYSES

### 7.1 Primary Effectiveness Hypothesis: to determine if addition of TENS to routine PT improves movement-evoked pain (MEP) in patients with fibromyalgia (FM).

Primary objective: To conduct an effectiveness analysis comparing the TENS+PT and PT only groups.

The raw data for both treatment groups will be presented graphically, and summarized as in the following table:

**Table 7.1: Descriptive Statistics of Movement-evoked Pain Over Time**

Visit	TENS+PT (N = XX)	PT Only (N = XX)
Baseline Pre-TENS		
Mean (SD)	XX.X (XX)	XX.X (XX)
(Min, Max)	(XX.X, XX.X)	(XX.X, XX.X)
Missing	XX	XX
Day 30 Post-TENS (Month = 1)		
Mean (SD)	XX.X (XX)	XX.X (XX)
(Min, Max)	(XX.X, XX.X)	(XX.X, XX.X)
Missing	XX	XX
Day 60 Post-TENS (Month = 2)		
Mean (SD)	XX.X (XX)	XX.X (XX)
(Min, Max)	(XX.X, XX.X)	(XX.X, XX.X)
Missing	XX	XX
Day 65 Post-TENS (Month 2)	NA	
Mean (SD)		XX.X (XX)
(Min, Max)		(XX.X, XX.X)
Missing		XX
Day 90 Post-TENS (Month 3)		
Mean (SD)	XX.X (XX)	XX.X (XX)
(Min, Max)	(XX.X, XX.X)	(XX.X, XX.X)
Missing	XX	XX
Day 180 Post-TENS (Month 6)		
Mean (SD)	XX.X (XX)	XX.X (XX)
(Min, Max)	(XX.X, XX.X)	(XX.X, XX.X)
Missing	XX	XX

## 7.2 Analysis

To assess the effectiveness of TENS+PT compared to PT alone, we will compare the change in movement-evoked pain during 5TSTS from pre-TENS baseline to post-TENS at day 60. The null hypothesis can be evaluated based on an assessment of parameter estimates from a linear mixed effects model (LMM: Laird & Ware, 1982). This will be tested using LMM analysis with treatment group and movement-evoked pain level at baseline as fixed effects. Randomization will be stratified by the healthcare system and clinic size. The model will be adjusted for the fixed effect of clinic size. The proposed study involves multiple clinics under each healthcare system, which is a potential source of additional variation. Patients within a clinic tend to be correlated due to similarity of environment, e.g. because of getting PT treatment from the same set of physical therapists (Localio et al, 2001). Therefore, a random effect will be included for treatment nested within clinic, and within healthcare system.

For this analysis, the LMM can be written in the following manner:

$$Y_{ijk} = \beta_0 + \beta_1 X_{1i(jk)} + \beta_2 X_{2i(jk)} + \beta_3 T_{ijk} + a_{i(j)} + \epsilon_{ijk}$$

where:

- $Y_{ijk}$  is the change in movement evoked pain level from baseline to day 60 for the  $k^{\text{th}}$  participant in  $i^{\text{th}}$  healthcare system and  $j^{\text{th}}$  clinic.
- $\beta_0$  is the common intercept.
- $X_{1i(jk)}$  is the movement evoked pain level at baseline for the  $k^{\text{th}}$  participant .
- $X_{2i(jk)}$  if the participant was in the large clinical size strata at baseline, 0 otherwise.
- $T_{ijk} = 1$  if  $k^{\text{th}}$  participant in  $i^{\text{th}}$  healthcare system and  $j^{\text{th}}$  clinic is in the TENS+PT treatment group; = 0 otherwise.
- $a_{i(j)}$  is the random clinic effect within the  $i^{\text{th}}$  healthcare system
- $\epsilon_{ijk}$  is a random error term for the  $k^{\text{th}}$  participant in  $i^{\text{th}}$  healthcare system and  $j^{\text{th}}$  clinic.

From the fitted model, the difference in mean change on pain between the two treatment groups will be assessed by the test for treatment effect. Accordingly, the main parameter of interest is  $\beta_3$ , which corresponds to the estimate of the difference in mean change in MEP between the TENS+PT vs PT only groups, controlling for baseline pain. *To assess the effectiveness of TENS+PT as measured by the change in MEP between baseline and Month 2 (Day 60), we employ the LMM described above.* Assuming the linear model provides the best fit, a test for the statistical significance of the mean difference between the two groups (TENS+PT vs. PT only) will be carried out as follows:

$$H_0: \beta_3 = 0 \quad vs. \quad H_A: \beta_3 \neq 0$$

Statistical significance for efficacy of TENS+PT vs. PT alone will be based on a two-tailed test at the 0.05 significance level with treatment effect summarized as mean difference with associated 95% confidence interval. If this hypothesis is not rejected, then we will conclude that there is not sufficient evidence to conclude that the TENS+PT treatment group is efficacious on MEP during the first two months of the treatment period. If the null hypothesis is rejected, figures will be utilized to assess which of the treatment groups shows significant differences over time with respect to the MEP scores. Each null hypothesis can be evaluated with the corresponding likelihood ratio test. Rejecting the null hypothesis implies that there is enough evidence to conclude that the use of TENS+PT is efficacious in reducing MEP compared to PT alone.

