### 7.3. Missing Data for mITT Analyses

In the case of subject drop-out, reasons for subject drop-out will be recorded and compared between the two treatment groups. Subject characteristics and outcome measures collected prior to drop-out for those who drop-out will be compared to those who complete the study. The modified ITT analysis will include all consented participants in their assigned treatment arm that have completed baseline (day 1) home activities for the primary outcome. This will include those with missing follow-up data. Accordingly, the modified ITT analysis for the primary outcome measure of change in movement-evoked pain at day 60 includes participants with baseline data but with missing day 60 pain values, multiple imputation of the missing pain values will be conducted. Multiple imputation analyses assuming missing at random (MAR) will be performed using SAS PROC MI and SAS PROC MIANALYZE. To avoid imputation bias, all variables in the substantive analyses and, if feasible, other variables in the study database predictive of the missing values or influencing the cause of missing data will be included.

In addition to the MI analysis under MAR, since the data under analysis cannot distinguish if data is MAR or it is missing not at random (MNAR), sensitivity analysis will also be performed. Methods for sensitivity analysis such as marginal delta adjustment, conditional delta adjustment, reference-based controlled imputation, and other pattern mixture models will be considered. If needed, variables will be transformed to satisfy approximate normality before imputation and retransformed back to original scale.

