The original sample size calculation conservatively assumed the ICC values to change between 0.12 and 0.14, subjects to be enrolled from 12 clinics in each group, and approximately equal number of subjects to be enrolled from each clinic. During the conduct of the study, as clinics were recruited, some other clinics were deactivated. It was also observed that there was variability in the number of patients enrolled per clinic. This observed variability required the need to account for the variation in the number of enrolled participants per clinic in the sample size calculation. For this purpose, the coefficient of variation (CV), which is the ratio of standard deviation (sd) to the mean (CV = sd / mean), was used in the sample size calculation to represent variation in enrollment per clinic

The number of active clinics at the time of the ICC recalculation was 28, where 26 clinics (13 in each treatment) had at least one participant with a day 1 assessment. The observed CV was 0.6.

Plans for sample size recalculation were discussed with Drs. [name] and [name] from the NIH Collaboratory Biostatistics Core in November 2022. This meeting resulted in two recommendations: 1) recalculating the ICC value based on the adjusted model, consistent with the final analyses. 2) Calculating the ICC and the Jackknife estimate of standard error (SE) of ICC, and calculating the sample size using both the current estimate of ICC and ICC + 1SE as a conservative estimate.

These recommendations were included in the implementation of the interim ICC estimation and sample size recalculation. With 220 enrolled subjects, the estimate of the ICC based on the adjusted model, consistent with the SAP, was 0.05 with the Jackknife estimate of the SE of ICC of 0.07. Taking into account the variability in enrollment numbers per clinic (CV = 0.6) and using 13 clinics/group, the sample size was estimated at 450 enrolled subjects to obtain a final number of 342 participants completing day 60 based on a 24% dropout rate. This sample size provides >90% power for ICC = 0.05, 81% power for ICC = 0.10, and 78% power for ICC of 0.12 (ICC + 1SE = 0.05 + 0.07). The study sample was updated to 450, assuming an ICC value of 0.10. The sample size recalculation was presented to NIAMS and the DSMB. Both NIAMS and the DSMB recommended approval of the change in sample size.

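### The SAP 7.2 primary model leaves out healthcare system, a randomisation stratum, and names no between-clinic degrees of freedom for the test, the confidence interval or the pooling after imputation

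*SAP*

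**What the plan says.** Clinics are randomised within strata of health system and practice size (Protocol 3 and 9.1; SAP 4). SAP 7.2 repeats this and adjusts for one stratum only: "Randomization will be stratified by the healthcare system and clinic size. The model will be adjusted for the fixed effect of clinic size". The equation contains baseline pain, clinic size, treatment, one random clinic effect and error. Healthcare system appears only as an index. The same paragraph nevertheless says: "The proposed study involves multiple clinics under each healthcare system, which is a potential source of additional variation". It then says that "a random effect will be included for treatment nested within clinic, and within healthcare system".

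On testing, SAP 7.2 first says: "The null hypothesis can be evaluated based on an assessment of parameter estimates from a linear mixed effects model". It then sets a two-tailed 0.05 test of β3 with a 95% confidence interval, and adds: "Each null hypothesis can be evaluated with the corresponding likelihood ratio test".

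For participants with no day 60 value, SAP 7.3 says: "Multiple imputation analyses assuming missing at random (MAR) will be performed using SAS PROC MI and SAS PROC MIANALYZE". The imputation is to contain "all variables in the substantive analyses and, if feasible, other variables in the study database predictive of the missing values".

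None of these places, nor Protocol 9.4, gives denominator df or a small-sample correction. The Protocol 9.4 mixed model also has no system term.

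**The concern.** Treatment is allocated to clinics, so the information on β3 is limited by the number of clinics. With about 26, two choices affect the p-value and the interval: whether the stratum is in the model, and which reference distribution is used. The plan omits the first in its equation and leaves the second open.

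The two gaps pull in opposite directions. A chi-square or normal reference is too liberal with few clinics. Leaving out a stratum that was balanced by design leaves its variance in the error term, which makes the test conservative when systems differ. The true level therefore depends on how much of the clinic variance lies between systems, which the documents do not give. At stake are a borderline primary result, the width of its interval and possibly some power.

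**Working it through.** **Inputs from the documents.** Two-sided α 0.05, difference 1.0, SD 2.0, 13 clinics per arm, 342 completers, CV of clinic size 0.6, ICC 0.05, 0.10 and 0.12 (SAP 9); 6 health systems (Protocol 3).

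**Assumptions.** The split of clinics over systems, and the share of clinic variance between systems.

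**1. The plan's own power.** With n = 342/2 = 171 per arm, m = 171/13 = 13.15. Design effect = [1 + (m − 1)ICC] / [1 − CV²·L(1 − L)], with L = m·ICC/(m·ICC + 1 − ICC). At ICC 0.10:

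- L = 1.315/2.215 = 0.594
- design effect = 2.215/(1 − 0.36 × 0.594 × 0.406) = 2.426
- effective n = 171/2.426 = 70.5 per arm
- noncentrality = 1/(2√(2/70.5)) = 2.97

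| ICC | Stated | t on 26 − 2 = 24 df | Normal reference |
|---|---|---|---|
| 0.05 | >90% | 91.6% | 93.6% |
| 0.10 | 81% | 81.3% | 84.3% |
| 0.12 | 78% | 77.3% | 80.6% |

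The stated power is reproduced closely on between-clinic df.

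**2. Size at the boundary.** The written equation has three clinic-level terms (intercept, size, treatment), so df = 26 − 3 = 23. Five system terms leave 18. A statistic at the normal 5% limit (1.960) has p = 0.062 on 23 df and 0.066 on 18 df. The interval is 2.069/1.960 = 1.055 or 2.101/1.960 = 1.072 times as wide, if the estimate and standard error are held fixed.

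**3. Type I error on complete data.** The SAP equation was simulated with β3 = 0: 26 clinics, 342 participants, CV 0.6, systems of 6, 4, 4, 4, 4 and 4 clinics, treatment balanced within system, 10,000 trials per row (Monte Carlo SE about 0.2 points, 0.3 at the highest rates). LRT is the likelihood ratio test; share is the part of clinic variance between systems.

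| Share, ICC | As written: LRT | As written: Wald z | As written: t(23) | System fixed: LRT | System fixed: t(18) |
|---|---|---|---|---|---|
| 0, 0.05 | 7.1% | 6.6% | 5.3% | 10.3% | 5.4% |
| 0, 0.10 | 7.2% | 6.6% | 5.3% | 11.5% | 5.2% |
| 0, 0.12 | 7.3% | 6.6% | 5.2% | 11.9% | 5.3% |
| 50%, 0.05 | 4.9% | 4.5% | 3.4% | 8.1% | 4.3% |
| 50%, 0.10 | 4.0% | 3.6% | 2.8% | 10.4% | 4.6% |
| 50%, 0.12 | 3.8% | 3.5% | 2.7% | 10.7% | 5.1% |

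A separate set of 20,000-trial runs gave, for the written equation with the LRT and balanced systems, 6.7 to 7.1% at share 0, 4.9 to 5.5% at 30% and 3.2 to 4.4% at 60%. With unbalanced systems the ranges were 6.8 to 7.5%, 5.5 to 6.0% and 4.1 to 5.6%.

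**4. Imputed route.** The SAP equation was pooled with no complete-data df supplied (12 or 20% of day 60 values missing, an assumption; 4,000 trials, SE about 0.3 points). The level was 1.5 to 5.5% with clinic as a class variable in the imputation, and 3.0 to 7.0% with clinic as a random intercept.

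**5. Power at ICC 0.10.** t test on the written equation against t test with system fixed:

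| Layout, share | As written | System fixed | Change (points) |
|---|---|---|---|
| Balanced, 0 | 80.9% | 79.4% | −1.5 |
| Unbalanced, 0 | 79.8% | 74.8% | −5.0 |
| Balanced, 30% | 83.0% | 86.1% | +3.1 |
| Balanced, 60% | 85.7% | 92.8% | +7.1 |

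**The case against.** A reader might infer that the primary test runs at about 7%. The documents do not support that. The likelihood ratio test is permitted, not required, and the committed result is a two-tailed test of β3 with an interval. SAP 7.3 makes the mITT result an imputed estimate pooled in MIANALYZE, which combines estimates and standard errors, not likelihood ratios. On that route there is no clear inflation with clinic as a class variable. The 7.0% upper figure needs a random-intercept imputation that the SAP does not name.

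A reader might also infer that omitting healthcare system inflates the error or biases the effect. It does neither here: with treatment balanced within systems, the omission lowers the level.

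Nor does the prose clearly commit to two random effects. "a random effect will be included for treatment nested within clinic, and within healthcare system" speaks of one effect, and a single clinic-within-system term fits it. What is malformed is treatment nested within clinic, because treatment is constant within a clinic.

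It is fair to add that the stated 81% and 78% power fit a t test on 24 df, so the missing df may be a drafting omission. Intent is not settled, since the original sample-size table reproduces without between-clinic df. The 18-df boundary figure holds the estimate and standard error fixed, and both would move once system is added.

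What stands: a stratum is missing from the equation, and the reference distribution of the primary test is unspecified.

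**Conclusion.** The point holds, at modest size. With about 26 clinics, the level of the written equation on complete data is about 7% (likelihood ratio) or 6.6% (Wald z) if systems do not differ. If half or more of the clinic variance lies between systems and arms are balanced within them, it falls to roughly 3 to 5% with the likelihood ratio test and about 3% on t(23). A t test with system fixed stays at 4.3 to 5.4% in the same simulations, so its level does not depend on the unknown share.

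The consequence is mainly for results near p = 0.05 and for interval width. The sample size and stated power are not challenged.

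These figures rest on the interim count of 26 clinics (Protocol 3 plans 25 to 35, and SAP 9 notes that "as clinics were recruited, some other clinics were deactivated"), on assumed system layouts and variance shares, and on fixed df of 23 and 18 standing in for Kenward-Roger or Satterthwaite values.

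**What to change.** Make these edits together and before unblinding. Adding system while keeping the likelihood ratio test gives 8.1 to 11.9%.

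- **SAP 7.2:** add healthcare system as a fixed effect beside clinic size. Keep one random clinic intercept and correct the nesting wording. Delete the likelihood ratio sentence. Test β3, with its 95% interval, by the REML t test with Kenward-Roger or Satterthwaite df. State how a system with clinics in only one arm will be pooled.
- **SAP 7.3:** say explicitly that clinic is in the imputation model and in what form. Give MIANALYZE the clinic-based complete-data df (26 − 3 − 5 = 18 for 26 clinics and 6 systems). With 18 df, clinic as a class variable remains conservative (1.7 to 4.4%).
- **Protocol 9.4:** align the model with the SAP.

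The work is wording and program options. The price is power if systems do not differ: at ICC 0.10, about 1.5 points with balanced systems and up to about 5 with unbalanced ones, which takes power to about 79% or 75%. If 30 to 60% of clinic variance lies between systems (balanced layout), power rises by about 3 to 7 points.

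If only the minimum is adopted, dropping the likelihood ratio test and naming a t test on between-clinic df keeps the complete-data level at about 5% or below and fits the stated power. It leaves the possible loss of efficiency from the omitted stratum.

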### 7.3. Missing Data for mITT Analyses

In the case of subject drop-out, reasons for subject drop-out will be recorded and compared between the two treatment groups. Subject characteristics and outcome measures collected prior to drop-out for those who drop-out will be compared to those who complete the study. The modified ITT analysis will include all consented participants in their assigned treatment arm that have completed baseline (day 1) home activities for the primary outcome. This will include those with missing follow-up data. Accordingly, the modified ITT analysis for the primary outcome measure of change in movement-evoked pain at day 60 includes participants with baseline data but with missing day 60 pain values, multiple imputation of the missing pain values will be conducted. Multiple imputation analyses assuming missing at random (MAR) will be performed using SAS PROC MI and SAS PROC MIANALYZE. To avoid imputation bias, all variables in the substantive analyses and, if feasible, other variables in the study database predictive of the missing values or influencing the cause of missing data will be included.

In addition to the MI analysis under MAR, since the data under analysis cannot distinguish if data is MAR or it is missing not at random (MNAR), sensitivity analysis will also be performed. Methods for sensitivity analysis such as marginal delta adjustment, conditional delta adjustment, reference-based controlled imputation, and other pattern mixture models will be considered. If needed, variables will be transformed to satisfy approximate normality before imputation and retransformed back to original scale.

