In the case of subject drop-out, reasons for subject drop-out will be recorded and compared between treatment groups. Subject characteristics and outcome measures collected prior to drop-out for those that drop-out will be compared to those that complete the study. In the presence of missing data, under the assumption of missing at random (MAR), linear mixed model analysis, which can handle incompletely observed subjects and uses a likelihood estimation method, will provide correct likelihoods and lead to valid estimates. However, since the data under analysis cannot distinguish if data is MAR or it is missing not at random (MNAR), sensitivity analysis will also be performed. Methods for sensitivity analysis such as marginal delta adjustment, conditional delta adjustment, reference-based controlled imputation, and other

pattern mixture models will be considered. If needed, variables will be transformed to satisfy approximate normality before imputation and retransformed back to original scale. To avoid imputation bias, all variables in the substantive analyses and, if feasible, other variables in the study database predictive of the missing values or influencing the cause of missing data will be included. Multiple imputation analyses using SAS PROC MI and SAS PROC MIANALYZE will be conducted. Any differences in results of the primary analysis and the sensitivity analyses, and possible reasons will be reported.

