## 9. SAMPLE SIZE JUSTIFICATION

The required sample size was calculated to assess the effect of TENS+PT versus PT alone on the primary outcome of change from baseline to 2-month visit in pain after PT using two-independent samples t-test with inflation factor of  $[1+(m-1)*ICC]$  applied to account for average cluster size (m) and intra-cluster correlation (ICC). From the FAST study, there was a standard deviation of 2 for change in movement-evoked pain for the 5TSTS test. There was a greater decrease in pain with active- TENS compared to placebo-TENS of 1.3 (95% CI: 0.34, 2.2) for movement-evoked pain during 5TSTS. Compared to no-TENS, there was a greater decrease in pain with active-TENS of 1.8 (95% CI: 1.0, 2.8) for movement-evoked pain during 5TSTS. For this cluster randomized pragmatic trial comparing TENS+PT vs. PT alone, sample size was determined such that the statistical test at the 0.05 significance level will be able to detect a difference of at least 1.0 in mean change in pain with 80% power. Participants randomized to a treatment arm will be clustered by clinic, since PT clinics will be randomized for ease of implementation. Thus, an estimate of the intra-cluster correlation (ICC) was needed for the sample size calculation. With no prior estimate of ICC, the required sample size per treatment arm (or participants per clinic) for the desired detectable mean difference of 1.0, assuming SD=2.0, was calculated for combinations of ICC values and number of clinics per treatment arm; see Table 1 for ICC values for a sample size <300 participants per treatment arm. A pilot study examining a non-pharmacological intervention for pain by our group showed an ICC of 0.01, DeBar and colleagues used an ICC of 0.002 for sample size calculation for a chronic pain population, and Adams et al. showed widely varying ICCs between data sets, but the majority of patient-reported outcomes were below 0.095 ICC. Therefore, the study sample size was originally calculated for ICC value between 0.12 and 0.14 which resulted in a conservative sample size estimate of 456 total participants (228 per treatment arm) with complete data, for 9 to 12 clinics per arm. Table 9.1 shows the number of participants per clinic for each treatment arm, for specified ICCs and range of 9 to 12 clinics per treatment arm (C), to detect a mean difference of at least 1 (in NRS scale of 0 to 10) in pain at the 0.05 significance level with 80% power. Numbers in black are the sample size needed for combinations of ICCs and number of clinics for  $n \leq 228/\text{arm}$  while the tan numbers are for  $n > 228$  per treatment arm.

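### SAP 7.3 imputes missing Day 60 pain without carrying the random clinic effect of SAP 7.2, so the primary standard error can be wrong in either direction

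*SAP*

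**What the plan says.** SAP 7.2 models change in movement-evoked pain from baseline to Day 60 on treatment, baseline pain and clinic size, with a random clinic effect within healthcare system. Its reason is that "Patients within a clinic tend to be correlated due to similarity of environment". The treatment effect "will be based on a two-tailed test at the 0.05 significance level"; no reference degrees of freedom are given.

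SAP 1.1 and 6.1.1 make the modified ITT set primary: everyone who completed the Day 1 home activities. SAP 7.3 keeps participants without a Day 60 score in that analysis by imputation: "Multiple imputation analyses assuming missing at random (MAR) will be performed using SAS PROC MI and SAS PROC MIANALYZE". The imputation model is to contain "all variables in the substantive analyses and, if feasible, other variables in the study database predictive of the missing values". Nothing says whether clinic enters, or in what form. SAP 7.3 also lists delta-adjusted and reference-based sensitivity analyses, and SAP 8 applies the section 7 methods to every secondary outcome.

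Protocol 9.4 differs. It relies on the likelihood-based mixed model as valid under MAR, then turns to sensitivity analysis, and in that later text says "Multiple imputation analyses using SAS PROC MI and SAS PROC MIANALYZE will be conducted".

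**The concern.** An imputation model should reproduce the structure that the analysis model then estimates. Here that structure is between-clinic variation, which drives the standard error in a cluster-randomised trial.

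- **Clinic omitted.** Imputed values scatter around the arm's regression line and carry no clinic effect. If a share p is missing, each clinic mean keeps only (1 − p) of its own effect, so the between-clinic variance in the completed data falls by about (1 − p)²: 0.76² = 0.58 at 24% missing. The treatment estimate still carries the full clinic variation. Rubin's rules do not restore the loss.
- **Clinic as a fixed effect.** Imputation noise enters each clinic mean and shows up as between-clinic spread in every completed data set. Rubin's rules then add it again as between-imputation variance.

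At stake is the single confirmatory test. The first choice gives intervals that are too narrow; the second gives up power. The same imputation would feed the secondary and MNAR analyses.

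**Working it through.** **Inputs.** SAP 9: "there was a standard deviation of 2 for change in movement-evoked pain for the 5TSTS test"; the test "will be able to detect a difference of at least 1.0 in mean change in pain with 80% power"; a "two-independent samples t-test with inflation factor of" 1 + (m − 1)·ICC; 13 clinics per arm; CV of clinic size 0.6; interim ICC 0.05 (jackknife SE 0.07); planning ICC 0.10, conservative value 0.12; 450 enrolled, 342 with Day 60, 24% dropout. Assumption: 12% missing as a lower case, borrowed from the FAST 30-day dropout, because the documents do not split the 24% into losses before and after baseline.

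**Step 1: the plan's own figures.** 342/0.76 = 450. With m = 342/26 = 13.15 and k = 13, DEFF = 1 + [(CV²(k − 1)/k + 1)·m − 1]·ICC = 1.83, 2.65 and 2.98 at ICC 0.05, 0.10 and 0.12. The effective n per arm is 171/DEFF = 93.6, 64.5 and 57.3. Power = Φ(0.5·√(n/2) − 1.96) = 92.8%, 81.0% and 76.3%. The plan states >90%, 81% and 78%, so its figures reproduce within 2 points. It states no standard error or type I error for the imputed analysis.

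**Step 2: hand check at ICC 0.10 and 24% missing.** Take equal clinics, no covariates and 20 imputations. Between-clinic variance is 0.4 and within-clinic variance 3.6. Each clinic has 450/26 = 17.31 participants, 13.15 of them observed.

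- True variance = (2/13)(0.4 + 3.6/13.15) = 0.1036.
- Clinic omitted: W = (2/13)[0.76²·0.4 + (0.76·3.6 + 0.24·4)/17.31] = 0.0684; B = 2(0.24·4/225 + 0.24²·4/171) = 0.0112; T = W + 1.05·B = 0.0802. SE ratio = √(0.0802/0.1036) = 0.88.
- Clinic fixed: imputation noise per clinic mean = 0.24²·3.6/13.15 + 0.24·3.6/17.31 = 0.0657; W = (2/13)(0.4 + 0.2737 + 0.0657) = 0.1137; B = (2/13)(0.0657) = 0.0101; T = 0.1244. SE ratio = √(0.1244/0.1036) = 1.10.

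**Step 3: simulation under no treatment effect.** 6,000 trials per setting; 26 clinics, CV 0.6, SD 2; REML random-intercept model adjusted for baseline and clinic size; 20 imputations pooled by Rubin's rules; missing completely at random; no Day 30 predictor. N is 450 at 24% missing and 342/0.88 = 389 at 12%. Each cell gives mean model SE divided by the empirical SD of the estimates, then type I error with cluster-level df. For example, 0.2966/0.3408 = 0.87.

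| ICC, missing | Clinic omitted | Clinic fixed | Clinic random | Mixed model, observed data |
|---|---|---|---|---|
| 0.05, 24% | 0.91; 5.9% | 1.15; 2.2% | 1.00; 4.4% | 0.99; 5.0% |
| 0.10, 24% | 0.87; 8.0% | 1.11; 2.8% | 1.00; 5.0% | 1.00; 5.6% |
| 0.12, 24% | 0.86; 8.0% | 1.10; 2.8% | 1.00; 4.9% | 1.00; 5.3% |
| 0.05, 12% | 0.96; 5.2% | 1.08; 3.0% | 1.01; 4.3% | 1.00; 4.6% |
| 0.10, 12% | 0.92; 6.6% | 1.05; 4.0% | 0.99; 5.1% | 0.99; 5.4% |
| 0.12, 12% | 0.92; 6.6% | 1.05; 4.0% | 1.00; 5.3% | 0.99; 5.4% |

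Monte Carlo error is about 0.3 points near 5%. A second simulation of the same layout (t with 24 df) gave, with clinic omitted, ratios of 0.87–0.89 and 0.93–0.94 at 24% and 12% missing (errors 7.2–8.7% and 6.2–7.9%). With clinic fixed it gave 1.11–1.12 and 1.05–1.07 (2.7–3.4% and 3.7–4.7%). The observed-data mixed model gave 5.2–6.1%.

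**Step 4: two modifiers.** With Rubin's large-sample df instead of cluster-level df, the clinic-omitted error at 24% missing rises to 7.9%, 10.1% and 9.9% across the three ICCs. In the other direction, when Day 30 pain was complete, carried the full clinic effect and was used as a predictor, the clinic-omitted error fell to 5.0–6.0%.

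**Step 5: power if clinic is fixed.** At ICC 0.10 and 24% missing, an SE overstated by 11% moves the critical value from 1.96 to 1.96·1.11 = 2.18. The stated 81% power corresponds to a standardised effect of 1.96 + 0.88 = 2.84, so power becomes Φ(2.84 − 2.18), about 75% (normal approximation, true SE unchanged).

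**The case against.** Several objections have force.

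- SAP 7.3 never says that clinic is left out, and its instruction to include the analysis variables can be read as including it. That stands. A reader might infer that the 5% test is necessarily inflated; the documents do not support this. With clinic entered as a fixed class term the test is conservative. But the wording does not settle the matter: clinic is a random effect in SAP 7.2, and neither ordinary reading gives the right standard error.
- A reader might take 24% as the missing share of the primary set. It is not. SAP 9 counts in it consented patients who never complete baseline, and SAP 6.1.1 excludes them. If half the losses fell before baseline (an assumption), the set would be 396 with 54 missing, or 13.6%.
- A reader might infer that naming PROC MI leaves only these two versions. The documents do not say what the procedure can fit, and SAP 7.3 allows further predictors, which could include Day 30 pain. The point rests on what the SAP leaves unsaid, not on a software limit. The Day 30 rescue is a favourable case: early dropouts may also lack Day 30, and such predictors are included only where feasible.
- At ICC 0.05 and 12% missing the effect of omission is slight (5.2%). That stands for this setting; at the planning ICC of 0.10 the main run gives 6.6%.

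**Conclusion.** The concern holds as an error in the error bars whose direction is open. As written, SAP 7.3 does not carry the clinic effect that SAP 7.2 requires. Across the two simulations, at ICC 0.05 to 0.12:

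- clinic omitted: SE about 9–14% too small and type I error about 6–9% at 24% missing, the upper bound; about 4–8% and 5–8% at the assumed 12%;
- clinic fixed: SE about 5–15% too large and type I error about 2–5%.

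These figures assume normal outcomes, missingness completely at random, 26 clinics with CV 0.6, cluster-level df and no Day 30 predictor. A complete Day 30 score that carries clinic information would shrink the bias. Random-clinic imputation and the observed-data mixed model both hold close to 5% in the main run. Separately, Protocol 9.4 and SAP 7.3 disagree on whether imputation is the primary analysis or a sensitivity analysis. This should be fixed. It does not show that the final test will exceed 5%.

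**What to change.** In SAP 7.3, choose one of two routes.

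1. Make the likelihood-based mixed model on observed data the primary mITT analysis, as Protocol 9.4 implies, with multiple imputation as sensitivity. State which form is meant. The single-outcome model of SAP 7.2 uses only participants with a Day 60 score. The repeated-measures model of Protocol 9.4 can also use those with Day 30 only. The simulation covered the first form.
2. Keep imputation as primary, but specify a two-level model with a random clinic intercept and baseline pain, Day 30 pain, treatment, clinic size and healthcare system as predictors, followed by the same mixed model and pooling.

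Under either route, use the same clinic-aware imputation for the delta and reference-based analyses, state between-clinic degrees of freedom for the treatment test, and reconcile Protocol 9.4 with SAP 7.3 on the role of imputation.

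Cost: SAP and protocol wording, with no new data and no more participants. Route 2 is likely to need one imputation routine outside PROC MI, which the trial's programmers should confirm. Route 1 needs none for the primary analysis.
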